2.1 Study Overview

To investigate the clinical efficacy of abdominal acupuncture in promoting gastrointestinal functional recovery following gynecologic laparoscopic hysterectomy, with the aim of reducing postoperative complications, enhancing postoperative quality of life, and providing a safe, convenient, and effective therapeutic strategy for clinical practice.

2.2 Background

Postoperative gastrointestinal dysfunction (POGD), commonly referred to as postoperative ileus (POI), is a well-recognized complication¹。 Contemporary studies indicate that POI typically persists for 3–5 days and is characterized by transient impairment of gastrointestinal tract (GIT) function following abdominal surgery. Its pathological manifestations primarily involve mucosal injury, disruption of barrier integrity, and impaired gastrointestinal motility. Clinically, patients may present with a wide spectrum of symptoms, including nausea, vomiting, abdominal pain, diarrhea, defecatory difficulties, and diminished or absent bowel sounds^{2,3}.

The pathogenesis of this condition is multifactorial, encompassing surgical techniques and manipulation, disturbances of internal homeostasis, alterations in blood perfusion, anesthetic and analgesic regimens, inflammatory responses, and neuroendocrine mechanisms. In addition, unique physiological characteristics in gynecologic patients, unfavorable psychological states, and surgical positioning further elevate the risk of POGD, underscoring the critical importance of prevention and management⁴⁻¹¹。 Current Western medical approaches comprise supportive measures (such as enemas and fluid replacement), pharmacotherapy (e.g., metoclopramide hydrochloride, mosapride), endoscopic interventions, gastrointestinal pacing devices, and surgical

procedures. However, drug-related adverse effects—including somnolence, agitation, and paradoxical gastrointestinal symptoms—remain prevalent, while invasive procedures carry inherent risks and may even exacerbate gastrointestinal dysfunction. In contrast, traditional Chinese medicine (TCM) has demonstrated encouraging outcomes in the management of POGD. Treatment modalities include oral herbal preparations, acupuncture, moxibustion, herbal enemas, and acupoint injections. These therapies, mainly employed as adjunctive interventions, offer the advantages of individualized pattern-based treatment, clear therapeutic efficacy, high safety, and relatively low cost. Nonetheless, challenges persist, such as reliance on practitioner experience, methodological limitations in clinical research, lack of standardized diagnostic criteria, incomplete elucidation of therapeutic mechanisms, and insufficient safety evaluation. At present, studies specifically targeting gastrointestinal dysfunction after gynecologic laparoscopy remain scarce, and greater attention should be given to the potential of TCM-based strategies to enhance patients' overall postoperative quality of life by leveraging their simplicity, accessibility, and cost-effectiveness.

Abdominal acupuncture, as both an inheritance and an innovation of traditional acupuncture, has been increasingly applied in clinical settings due to its broad indications, minimal discomfort, stable efficacy, and rapid onset of action¹²⁻¹⁴. It operates primarily through the stimulation of specific abdominal acupoints, thereby harmonizing congenital and acquired Qi to restore physiological balance. Among various approaches, Bo's abdominal acupuncture is most widely utilized. By capitalizing on the therapeutic advantages of abdominal acupoints, this technique

enhances gastrointestinal peristalsis, facilitates gastric emptying, accelerates the recovery of gastrointestinal hormones, and ultimately promotes restoration of gastrointestinal function. Compared with conventional Chinese and Western medical interventions, abdominal acupuncture offers fewer adverse effects, technical simplicity, reduced financial burden, and an ability to avoid the unpleasant sensations of soreness, numbness, distension, or pain associated with traditional body acupuncture, thus highlighting its unique clinical value. This study is therefore designed to investigate the impact of abdominal acupuncture on gastrointestinal functional recovery and long-term quality of life in patients undergoing gynecologic laparoscopic hysterectomy, with the ultimate aim of providing a safer, simpler, and more effective therapeutic modality for the management of postoperative gastrointestinal dysfunction.

2.3 Study Objective

To explore the clinical efficacy and safety of abdominal acupuncture therapy in promoting gastrointestinal function recovery after gynecological laparoscopic surgery.

2.4 Methodology

2.4.1 Trial Design

This study was conducted as a single-center, randomized, controlled clinical trial in China. Ethical approval was obtained from the Ethics Committee of Guangdong Provincial Hospital of Chinese Medicine (Approval No. YF2023-435-01), and written informed consent was secured from all participants.

2.4.2 Patients

2.4.2.1 Patient Selection

Between December 2023 and December 2024, patients admitted to the Department of Gynecology at the Dade Road Branch of Guangdong Provincial Hospital of Chinese Medicine who underwent laparoscopic total hysterectomy, met the inclusion criteria, voluntarily agreed to participate, and signed the informed consent form provided by the investigators were enrolled in the study.

2.4.2.2 Diagnostic Criteria of Western Medicine

The diagnostic criteria for postoperative gastrointestinal dysfunction were established according to the *Expert consensus on prevention and treatment of postoperative gastrointestinal dysfunction*¹⁵:

- (1) Nausea or vomiting;
- (2) Inability to tolerate solid or semi-liquid food within 24 hours after surgery;
- (3) Absence of flatus or defecation within 24 hours postoperatively;
- (4) Abdominal distension;
- (5) Radiological evidence of POI.

A diagnosis can be established if any two of the above five criteria are present.

2.4.2.3 Inclusion Criteria

- (1) Female patients who underwent gynecologic laparoscopic total hysterectomy under general anesthesia;
- (2) Age between 18 and 65 years;
- (3) Surgical duration ranging from 0.5 to 4.5 hours;
- (4) Anesthesia duration ranging from 1 to 5 hours;
- (5) Willingness to receive acupuncture therapy without a history of adverse reactions such as needle syncope;
- (6) Provision of signed informed consent.

2.4.2.4 Exclusion Criteria

- (1) Patients with comorbid conditions that may affect gastrointestinal function, including intestinal obstruction or space-occupying lesions of the digestive system;
- (2) Patients with severe systemic diseases, including hepatic or renal failure, cardiovascular or cerebrovascular disorders, infectious diseases such as HIV/AIDS, or severe psychiatric illness;
- (3) Individuals with a history of adverse reactions to acupuncture, including needle syncope;
- (4) Patients with local skin damage, rashes, or ulcers at the proposed acupoint sites;
- (5) Patients concurrently enrolled in other clinical studies.

2.4.2.5 Dropout Criteria

- (1) Patients who develop subcutaneous hematoma, skin damage, or rash at the primary acupoint sites during the trial, rendering acupuncture infeasible;
- (2) Patients who fail to comply with the prescribed treatment protocol or have incomplete data.

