2.4.2.6 Withdrawal Criteria

- (1) Patients who voluntarily request withdrawal from the clinical trial;
- (2) Patients lost to follow-up due to subjective or objective reasons.

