2.4.2.7 Criteria for Termination of Participation

- (1) Patients experiencing moderate to severe adverse reactions to acupuncture (e.g., needle syncope), or those unwilling to continue treatment;
- (2) Patients who develop serious adverse events or complications that preclude continuation of the study;
- (3) Patients who present with severe gastrointestinal dysfunction during the trial requiring alternative therapeutic interventions.

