2.4.3.3 Abdominal acupuncture treatment

The initial abdominal acupuncture treatment was performed 4–6 hours after surgery, followed by one session daily from postoperative day 1 through day 4, yielding a total of five sessions per treatment course. Throughout the treatment period and thereafter, patients' clinical conditions were systematically recorded and evaluated, with concurrent monitoring of adverse events and concomitant medication use.

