2.4.3.5 Patient Withdrawals

Patients may leave the study at their own discretion, and the investigator may determine if the patients withdraw from the trial due to violation of the trial protocol or the occurrence of a serious adverse event. Figure 1 shows the flow diagram of the trial.

[figure not shown]

Figure 1 Flow chart

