4.3 Efficacy Parameters

4.3.1 Clinical efficacy indices

- **Recovery of gastrointestinal motility** including time to first postoperative passage of flatus (recorded to the exact hour and minute), time to first postoperative bowel movement (recorded precisely), and restoration of bowel sounds.
- **Incidence of postoperative gastrointestinal dysfunction** related complications: including abdominal distension or pain, nausea, vomiting, and diarrhea.

All the above parameters were observed starting on the day of surgery and continued to be

recorded daily until the fifth postoperative day or discharge, whichever came first.

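### The dropout, termination and withdrawal rules merge stopping treatment with leaving the trial and are not reconciled with flatus recording to Day 5 or discharge (minor)

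*Protocol*

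**What the plan says.** Four sections of the protocol decide when a randomised patient stops counting as a participant.

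- **2.4.2.5 Dropout Criteria.** Item 1: "Patients who develop subcutaneous hematoma, skin damage, or rash at the primary acupoint sites during the trial, rendering acupuncture infeasible". Item 2: "Patients who fail to comply with the prescribed treatment protocol or have incomplete data".
- **2.4.2.6 Withdrawal Criteria.** Item 1: "Patients who voluntarily request withdrawal from the clinical trial". Item 2 covers loss to follow-up.
- **2.4.2.7 Criteria for Termination of Participation.** Item 1 covers moderate to severe reactions to acupuncture, "or those unwilling to continue treatment". Item 2 covers serious adverse events or complications. Item 3: "Patients who present with severe gastrointestinal dysfunction during the trial requiring alternative therapeutic interventions".
- **2.4.3.5 Patient Withdrawals.** Besides the patient's own choice, "the investigator may determine if the patients withdraw from the trial due to violation of the trial protocol" or a serious adverse event.

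Observation of the outcome is set elsewhere. Section 2.4.4 names time to first flatus as the primary outcome. Section 4.3.1 has it "recorded daily until the fifth postoperative day or discharge, whichever came first", with no condition on treatment. Section 2.4.3.3 gives a first session 4 to 6 hours after surgery, "followed by one session daily from postoperative day 1 through day 4". Section 2.4.4 adds 15% to the 33 per group for dropout or loss to follow-up, giving 38. Section 7 names tests but not the patients to whom they apply.

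**The concern.** Asking to leave the trial is its own event in 2.4.2.6, so refusing further needling must be something else. Section 2.4.2.7 nevertheless gives it the same consequence, the end of participation. A patient who refuses on Day 1 before passing flatus is then out under 2.4.2.7 but still to be recorded under 4.3.1, and site staff have no rule for choosing.

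Two kinds of loss could follow. Flatus may never be recorded, which no later analysis plan can repair. Or a recorded flatus time may be set aside because the patient carries the dropout label. The incomplete-data wording invites the second: read literally, it covers a patient who lacks only the quality-of-life score due 14 days after the last session (4.3.3).

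The reasons are not neutral between arms. Needle-site lesions and needling reactions arise in practice only under acupuncture. Severe gastrointestinal dysfunction can occur in either arm and is related to late flatus. Losses could therefore differ by arm and depend on the outcome.

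**Working it through.** **1. The rules set against the recording rule in 4.3.1**

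| Event | Section | Arm | Consequence stated | Flatus recording afterwards |
|---|---|---|---|---|
| Needle-site lesion | 2.4.2.5(1) | acupuncture in practice | dropout | not stated |
| Non-compliance, any incomplete data | 2.4.2.5(2) | either | dropout | not stated |
| Refuses further treatment | 2.4.2.7(1) | chiefly acupuncture | participation ends | not stated |
| Reaction to acupuncture | 2.4.2.7(1) | acupuncture in practice | participation ends | not stated |
| Severe gastrointestinal dysfunction | 2.4.2.7(3) | either | participation ends | not stated |
| Protocol violation | 2.4.3.5 | either | investigator may withdraw | not stated |

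Only 2.4.2.7 and withdrawal under 2.4.3.5, on their wording, plausibly end data collection. Section 2.4.2.5 attaches a label.

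**2. Inputs for scale**

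Section 2.4.4 gives control mean 37.60 h, SD 4.11 h, reduction 8.1 h, two-sided 5%, 90% power, 33 per group, 38 enrolled. The 38 reproduces: 33 × 1.15 = 37.95. The 33 does not follow from the stated SD: 2 × (1.960 + 1.282)² × 4.11² / 8.1² = 5.4, so 6 per group. The SD at which the formula gives 33 is 8.1 × √(33 / (2 × 3.242²)) = 10.15 h. I therefore show results at both SDs.

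**3. When is the primary outcome already known?**

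The Day 3 session falls at least 48 h after surgery. Share with flatus by 48 h, assuming normality:

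- Controls, SD 4.11: Φ((48 − 37.60)/4.11) = 0.994
- Controls, SD 10.15: Φ((48 − 37.60)/10.15) = 0.847
- Acupuncture at its planned mean, 37.60 − 8.1 = 29.5 h: Φ(18.5/10.15) = 0.97 at SD 10.15, and over 0.999 at SD 4.11

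A stop on Day 3 or 4 would thus rarely prevent flatus being observed. Its risk is that a known time is set aside. Early stops are where a time may never be recorded.

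**4. How much could it matter?**

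Simulation with no true effect: normal outcome, 38 per arm, pooled t-test at two-sided 5%, 200,000 trials per case. The numbers removed are assumptions; the protocol gives none.

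| Removed (one arm v other) | Shift (SD) | Type I error |
|---|---|---|
| None | 0.00 | 5.0% |
| 5 v 0, unrelated to flatus | 0.00 | 5.0% |
| 3 v 3, random from slower half | 0.00 | 4.5% |
| 4 v 2, random from slower half | 0.05 | 4.8% |
| 5 v 2, random from slower half | 0.08 | 5.6% |
| 5 v 0, random from slower half | 0.12 | 7.3% |

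Rough check on the last row: the slower half of a normal distribution averages √(2/π) = 0.798 SD above the mean, and 5 × 0.798 / 33 = 0.121, against 0.119 simulated. In hours, 0.119 × 4.11 = 0.49 h (6% of 8.1 h) and 0.119 × 10.15 = 1.2 h (15% of 8.1 h).

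**The case against.** Analysis sets are commonly left to a statistical analysis plan, which may exist and is not shown. A reader might infer that the protocol drops these patients from the primary analysis, especially as 2.4.4 counts dropout beside loss to follow-up. No section says so, and silence on the analysis set is not itself a fault here. That part of the objection stands.

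It can also be said that 4.3.1 is a general schedule, that the investigator's power in 2.4.3.5 is discretionary, and that 2.4.3.3 and 3.2.5 have the patient's condition documented during and after treatment. On that reading the sections are ambiguous rather than contradictory. This stands for 2.4.2.5. It does not dispose of 2.4.2.7, whose heading and content end participation without saying that recording goes on.

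Timing weakens the point further. Section 2.4.2.1 dates enrolment December 2023 to December 2024, the last assessment comes 14 days after a Day 4 session, and the first reference was accessed in September 2025. Follow-up is in all likelihood over, so changing the recording rule can no longer recover a flatus time.

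Finally, the arm-specific reasons have no documented link to flatus time, and arm-specific loss unrelated to the outcome gives no bias. The outcome-related reason applies to both arms. This stands, and it limits the size.

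**Conclusion.** The point holds as a minor one. Sections 2.4.2.5, 2.4.2.7 and 2.4.3.5 do not separate stopping treatment from leaving the trial, and none is reconciled with 4.3.1. Termination under 2.4.2.7, or withdrawal under 2.4.3.5, can end recording of the primary outcome early. The unlimited incomplete-data rule can class as a dropout a patient whose primary outcome is known.

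The plausible effect is small: type I error between 4.5% and 5.6% when slower patients are lost from both arms, and about 7.3% with a 0.12 SD shift when five are lost from one arm only. These figures rest on a normal outcome and assumed removal counts. They illustrate scale and do not predict this trial.

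Two stronger readings are not supported. One is that the rules favour acupuncture: the direction depends on who is lost from which arm, and the protocol does not determine it. The other is a serious inflation of error. Removing exactly the slowest five of one arm would give 0.24 SD and 20%, but no section implies that pattern.

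**What to change.** - Reconcile 2.4.2.5, 2.4.2.7 and 2.4.3.5 with 4.3.1: state that these events may end study treatment but do not end flatus recording, unless the patient withdraws consent. The clinical reasons for stopping treatment stay as they are.
- Limit the incomplete-data rule so that a missing secondary measure does not make a patient a dropout for the primary outcome.
- Analyse every recorded flatus time in the assigned arm, with a compliant-patient analysis as secondary.
- Report removals by arm, by reason, and by whether flatus had already been recorded.

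The cost is wording and analysis time. With follow-up apparently complete, the actionable part is to keep all flatus times already recorded and to report the removals; times never recorded stay missing. The downside is that non-compliers and times observed after other therapy are included. The estimate then reflects assignment rather than treatment received, and it may move in either direction.

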2.4.2.6 Withdrawal Criteria

- (1) Patients who voluntarily request withdrawal from the clinical trial;
- (2) Patients lost to follow-up due to subjective or objective reasons.

2.4.2.7 Criteria for Termination of Participation

- (1) Patients experiencing moderate to severe adverse reactions to acupuncture (e.g., needle syncope), or those unwilling to continue treatment;
- (2) Patients who develop serious adverse events or complications that preclude continuation of the study;
- (3) Patients who present with severe gastrointestinal dysfunction during the trial requiring alternative therapeutic interventions.

2.4.3 Trial Flow

2.4.3.1 Screening Visit

Patients will be screened according to inclusion and exclusion criteria, eligible patients will be required to provide written informed consent and enter the baseline visit. Randomization will be performed before baseline assessment.

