2.4.3.2 Baseline Visit

The investigators provided participants with postoperative recovery education and collected data on demographic information, clinical characteristics, assessment scales, and routine examinations.

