2.4.5 Randomization

Randomization was performed using SPSS version 26.0. To ensure reproducibility of the randomization process, a Random Number Seed was first applied, followed by the generation of random numbers using the UNIFORM(Max) function. These random numbers were then used to assign participants into groups, and a randomization table was created accordingly. During clinical implementation, participants were allocated sequentially according to their order of enrollment by matching them to the corresponding numbers in the randomization table, and the designated treatment protocol was applied. In this study, the intervention group received abdominal acupuncture, while the control group received standard care.

3. Interventions

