4.3.3 Relevant Assessment Scales

- **Pain assessment:** The Visual analogue scale (VAS) was applied (Appendix 1). Abdominal pain scores were recorded before and after treatment on the day of surgery (5 days after surgery).
- **Gastrointestinal symptom assessment:** Symptom scoring was based on the Perioperative Clinical Evaluation Standards for Gastrointestinal Motility (Guangdong Provincial Standard, Appendix 2). Scores were documented daily from the day of surgery (before treatment) through postoperative Days 1–5, according to observed gastrointestinal function.
- **Quality of life assessment:** The Gastrointestinal Quality of Life Index (GIQLI) was employed (Appendix 3). Assessments were performed on the day of surgery prior to treatment, on postoperative Day 5, and again on Day 14 following the final treatment session.

5. Adverse Events and Management

If adverse reactions occurred during the trial—such as needle stagnation, syncope, breakage, hematoma, or infection—investigators promptly managed the event, ensured patient safety, reassured the participant with an explanation, and documented the details in the case report form.

6. Ethical Principle

This clinical trial was reviewed and approved by the Ethics Committee of Guangdong Provincial Hospital of Traditional Chinese Medicine prior to participant enrollment (Approval No. YF-2023-435-01). The study was conducted in full compliance with the principles of the Declaration of Helsinki.

7. Statistical Analysis

Data were organized and managed using Microsoft Excel to establish a primary database, which was subsequently converted into an SPSS 26.0 database for statistical analysis. The Shapiro–Wilk test was employed to assess the normality of continuous variables. According to data distribution, descriptive statistics were presented as mean \pm standard deviation (SD) for normally distributed variables, and as median with interquartile range [P₂₅, P₇₅] for non-normally distributed variables. Between-group comparisons of normally distributed data were performed using independent-samples t tests, while within-group pre- and post-treatment comparisons were conducted using paired t tests. For non-normally distributed data, the Mann–Whitney U test was applied for between-group comparisons, and the Wilcoxon signed-rank test for within-group comparisons.

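### Randomisation is placed before the baseline assessment with no masking described, so nothing stated keeps the arm unknown when the pre-treatment VAS, symptom score and GIQLI are scored

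*Protocol*

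**What the plan says.** - **Order.** Protocol section 2.4.3.1 screens patients and then says that "eligible patients will be required to provide written informed consent and enter the baseline visit". Its next sentence is "Randomization will be performed before baseline assessment".
- **Content of the baseline visit.** Under section 2.4.3.2 the investigators "collected data on demographic information, clinical characteristics, assessment scales, and routine examinations".
- **Allocation.** Section 2.4.5 says that "participants were allocated sequentially according to their order of enrollment by matching them to the corresponding numbers in the randomization table". The comparator there is standard care.
- **Pre-treatment scores.** Section 4.3.3 gives each scale a value before the first session. For the VAS: "Abdominal pain scores were recorded before and after treatment on the day of surgery". For the symptom score: "Scores were documented daily from the day of surgery (before treatment) through postoperative Days" 1 to 5. For the GIQLI: "Assessments were performed on the day of surgery prior to treatment, on postoperative Day 5", and once more 14 days after the last session.
- **Analysis.** Section 7 plans paired tests within each group from before to after treatment, and repeated-measures ANOVA across time points. It also plans direct tests between the arms: "Between-group comparisons of normally distributed data were performed using independent-samples t tests", with a rank test as the alternative.

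**The concern.** A trial that compares needling with no needling usually cannot mask its post-treatment patient-reported scores. It can still obtain a baseline that is free of the arm, by recording it before anyone learns the allocation. The protocol fixes the opposite order and, in the text available, gives no reason for it.

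If the patient or the scorer knows the arm, a difference between arms in the pre-treatment scales has two possible sources: chance imbalance, or scoring influenced by the allocation. The data cannot separate them. The pre-treatment scales then become a weaker check of comparability and a weaker reference for change. The stake is how far results on the three secondary scales can be trusted as measured against a clean baseline.

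**Working it through.** No figure in the protocol bears on this point, so the check sets its statements side by side.

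**1. Are the pre-treatment scales scored after randomisation?** Section 2.4.3.1 puts randomisation before the baseline assessment, and section 2.4.3.2 puts the scales in the baseline visit. Section 4.3.3 dates the first VAS, symptom score and GIQLI to the day of surgery, before treatment. If these are the baseline-visit scales, they follow randomisation by rule. If they are a separate, later pre-treatment reading, they follow it as well.

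**2. Does anything described keep the arm unknown in between?**
- Section 2.4.1 names the design as single-centre, randomised and controlled, with no masking term.
- Section 2.4.5 reads the arm from a table by order of enrolment and mentions no concealment or delayed disclosure.
- Section 3.2.4 describes needling with an infrared lamp; no sham counterpart is described for the control arm.

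The text does not say when patient or scorer learns the arm. It also describes nothing that would prevent it.

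**3. Where do the values enter the analysis?**

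| Scale | Time points in section 4.3.3 | Paired pre-post test | First point of repeated-measures ANOVA |
|---|---|---|---|
| Symptom score | 1 + 5 = 6 | yes | yes, 1 of 6 |
| GIQLI | 1 + 1 + 1 = 3 | yes | yes, 1 of 3 |
| VAS | before and after treatment; number of occasions unclear | yes | only if measured repeatedly |

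The direct between-group tests of post-treatment values need not use the pre-treatment score at all.

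**4. What lies outside?** Section 2.4.4 names time to first flatus as the primary outcome; it has no baseline value. CRP, IL-6, TNF-α and SII (section 4.3.2) are laboratory values, not scored by judgement. This ordering reaches neither.

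**5. Where does randomisation fall relative to surgery?** No sentence in the text available says.
- Inclusion criteria 3 and 4 (section 2.4.2.3) limit operating and anaesthesia time, which can be verified only after surgery. Section 2.4.2.1 likewise mentions the operation before consent. Both suggest allocation after surgery.
- Section 4.3.2 schedules inflammatory markers before surgery, which suggests that the study starts earlier.
- Consent before surgery with randomisation after it would reconcile the two, but this is not stated. Figure 1 is not reproduced in the copy reviewed and may settle it.

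**The case against.** The strongest reply is that the baseline order adds little. Post-treatment scoring is open-label whatever is done, and that touches every between-group comparison of these scales. The protocol names no between-group test of change and no ANCOVA, so the pre-treatment value affects a comparison between arms only through the repeated-measures ANOVA. A shift in scoring that is equal before and after treatment would cancel in a change from baseline, and cleaning the baseline alone would then expose it. Enrolment is reported in the past tense for December 2023 to December 2024, and a reference was accessed in September 2025, so a reworded sequence may reach nobody.

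Most of this stands, and it limits the weight of the point. It does not remove it. The order is a rule the protocol states, a baseline taken before allocation is the sounder reference, and the order actually followed still governs how the results may be read.

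Three stronger readings are tempting, and the documents support none of them:
- A reader might infer that the arm was known and the scores were biased. The text shows only that no safeguard is described.
- A reader might try to size the bias from the points in Appendix 2 or the items in Appendix 3. No shift is given anywhere, and Appendix 2 does not say how each item is ascertained.
- A reader might conclude that patients were allocated before eligibility could be checked. The cues on timing conflict, and the missing figure may resolve them.

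**Conclusion.** The point holds as a minor one, for the secondary scales only. As written, the plan randomises before the baseline scales and describes nothing that keeps the arm unknown while they are scored. The pre-treatment VAS, symptom score and GIQLI should therefore not be presented as a baseline free of the allocation. No bias in the primary comparison or the laboratory markers follows from this ordering, and no size can be attached to any effect on the scales.

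This rests on two assumptions: that the stated order was the one followed, and that the parts of the document not available (Figure 1 and the removed front pages) describe no safeguard. The timing relative to surgery is a request for clarification, not a separate defect.

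**What to change.** **For any patient still to be randomised.** Reword section 2.4.3.1 so that all inclusion criteria, including both durations, are confirmed and the pre-treatment VAS, symptom score and GIQLI are completed before the allocation is revealed. State where randomisation falls relative to surgery. Having an assessor who does not know the arm would not be enough, because patients complete the VAS and GIQLI themselves.

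**For patients already randomised.** Do not rewrite the sequence. Report the order actually followed, including relative to surgery. If the baseline scales were taken after allocation, disclose it. Keep all patients in the analysis as randomised, and interpret both pre-post and post-treatment results on these scales as open-label.

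**Cost.** Prospectively, one step moves to just before the first session, with no extra visits or patients. Retrospectively, it takes a statement of the order and one disclosed limitation, with no new data. The limit of the change should be stated too: it protects the baseline only, post-treatment scores stay open-label, and bias in change from baseline is not removed.
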